**An RCT on Support Surfaces for Pressure Ulcer Prevention**

**NCT03351049**

**July 1, 2023**

## Study protocol

An individual randomized design will be used. Eligible acute care patients will be identified by a wound nurse and recruited within 48 hours of identification of moisture risk. New admissions will be screened for the pressure injury risk factors of Total Braden score  $\leq 18$  and Braden Moisture sub-scale score 1- constantly moist or 2-very moist, projected length of stay  $\geq 4$  days, and absence of pressure injuries. Total Braden  $\leq 18$  was found to represent a relative risk of pressure injury of 4.26 (95% CI, 3.27 to 5.55) in a meta-analysis of 31 studies. WOCN consensus guidelines for support surface selection indicate provision of a preventive support surface for those at risk, defined as Braden scale score  $\leq 18$ , and use of a surface with low air loss (LAL) features for those with Braden Moisture sub-scale score of 1 or 2. After informed consent, absence of pressure injuries will be confirmed, baseline data (biological and clinical data) will be recorded and participants will be randomized by the Clinical Coordinator (a wound and research nurse dedicated to this project) into one of seven groups differentiated only by the support surface assignment. Seven surfaces were chosen for the trial interventions that can be divided into reactive support surface with LAL or reactive surface without LAL and demonstrate a range of heat and moisture control performance characteristics. The Clinical Coordinator will carry out the randomization at the end of the baseline visit. Participants in all groups will be provided usual care including tissue integrity management according to study site system-wide Skin Integrity Procedures, which address risk assessment (daily), skin inspection (twice daily), regular patient repositioning (every two hours as condition allows), pressure alleviation, moisture control, nutritional support and friction/shear relief applications. This and the other aspects of usual care are adjuncts to the support surface intervention, which will be applied to all groups and documented. Data will be recorded daily by the Clinical Coordinator from assessments, electronic medical records, observations and interviews with clinical staff until pressure injury incidence or hospital discharge. We targeted a minimum projected length of stay of 4 days to allow sufficient time for a pressure injury to develop. Provision of the support surface intervention will be accomplished by coordination with the hospital's bed warehouse and local DME suppliers.

**Choice of outcomes:** The outcome measures were chosen to ensure direct relevance to patients at risk for developing pressure injuries. We chose the direct clinical outcome measure of pressure injury incidence to assess the clinical effectiveness of the study support surface interventions being compared. Pressure injury status will be monitored and recorded every day (7 days per week) until any of the following endpoints are reached: pressure injury incidence or discharge from hospital. Identification of pressure injury by certified wound nurses who are not part of the research team avoids potential bias and provides quality assurance. These nurses will not be blinded to surface type but will be blinded to surface performance characteristics. After an endpoint is reached, the pressure injury severity will be recorded as the highest stage reached prior to discharge (Stage 1, 2, 3, 4, deep tissue pressure injury (DTPI) or unstageable) as defined by NPUAP. If the pressure injury status was observed to be a DTPI or unstageable and later becomes stageable as 1, 2, 3, or 4, the latter stage will be recorded. Otherwise DTPI and unstageable injuries will be recorded as such.

**Choice of covariates:** Variables that may be associated with the outcome of pressure injuries were recorded and include:

- Relevant biological variables (recorded at baseline): age, sex, race, ethnicity, weight, height, and underlying health conditions such as diabetes, peripheral vascular disease, nutritional status, and incontinence
- Pressure injury risk factors (assessed and recorded daily until endpoint): Braden score, Braden subscale scores
- Clinical conditions and procedures (monitored and recorded daily until endpoint): layers of linens, type and length of the surgery,
- Length of stay and number of days on the support surface (recorded at study endpoint).

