### **Statistical Analysis Plan**

The effectiveness of reactive support surfaces with and without low air loss were compared. This was done using using a Pearson Chi-Square analysis to test for an association between treatment groups (2 levels - low air loss vs without low air loss) and pressure injury incidence.

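### Does the unstated start of the 4-day projected stay, combined with the 48-hour recruitment window, weaken the incidence comparison?

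*Combined protocol and SAP*

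**What the plan says.** The Study protocol section lists a projected stay of at least 4 days among the entry criteria, in a sentence that begins "New admissions will be screened for the pressure injury risk factors". The stated reason is "We targeted a minimum projected length of stay of 4 days to allow sufficient time for a pressure injury to develop". Patients are "recruited within 48 hours of identification of moisture risk", so the window opens at risk identification and not at admission. Just before allocation one criterion is rechecked: "After informed consent, absence of pressure injuries will be confirmed". Then "The Clinical Coordinator will carry out the randomization at the end of the baseline visit". Under Choice of outcomes, follow-up ends at pressure injury or discharge.

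Choice of covariates includes "Length of stay and number of days on the support surface (recorded at study endpoint)", which treats the two durations as separate items. The Statistical Analysis Plan consists of one Pearson chi-square test, used to "test for an association between treatment groups (2 levels - low air loss vs without low air loss) and pressure injury incidence". It lists no descriptive summaries of any kind.

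**The concern.** The 4-day minimum exists to give an injury time to appear, but the text does not tie it to the moment the assigned surface comes into use. Read from admission or from risk identification, the criterion can be met by a patient who has used up to 2 of the 4 days before randomisation. Remaining projected stay is not said to be rechecked at that point.

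Such patients would add to the denominator with little chance of an event. If there were many of them, incidence would be lower than the design intended and the test would lose power. Incidence is also analysed as a plain proportion, with no summary of days on the surface by group promised, so a reader might not know how much exposure lies behind it. Sites could also apply the criterion differently.

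**Working it through.** **1. Days left.** The inputs are the 4-day minimum and the 48-hour (2-day) window, both from the Study protocol section. Days left = 4 − (days from the start of the count to randomisation). Delays from admission to risk identification are assumed.

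| Count starts at | Recruited at once | Recruited at 48 h |
|---|---|---|
| Admission, risk identified on arrival | 4 | 4 − 2 = 2 |
| Admission, risk identified 1 day later | 3 | 4 − 1 − 2 = 1 |
| Admission, risk identified 2 days later | 2 | 4 − 2 − 2 = 0 |
| Risk identification | 4 | 4 − 2 = 2 |
| Randomisation | 4 | 4 |

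The figure of 2 days is therefore right on two readings, but only for a patient who is both at the minimum stay and recruited at the limit.

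**2. Bias.** Every delay in the table precedes randomisation. Remaining projected stay is thus a baseline characteristic, with the same expected distribution on each surface and in each of the two pooled groups.

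**3. Effect measure.** The documents give no hazard. Assume constant hazards of 0.02 and 0.01 per day, with risk = 1 − exp(−h·t).

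- t = 4: 0.0769 and 0.0392, ratio 1.96.
- t = 2: 0.0392 and 0.0198, ratio 1.98.

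**4. Power.** The documents state no sample size or power, so there is no figure to reproduce. Assume two equal groups, two-sided 0.05 and 80% power when nobody loses days. With p̄ = (p₁ + p₂)/2:

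n per group = [1.96·√(2p̄(1−p̄)) + 0.842·√(p₁(1−p₁) + p₂(1−p₂))]² / (p₁ − p₂)²

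Power = Φ{[(p₁ − p₂)·√n − 1.96·√(2p̄(1−p̄))] / √(p₁(1−p₁) + p₂(1−p₂))}

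A share s of patients drops from 4 days to 2, and the rest stay T days. With T = 4, n is 604 per group.

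Worked example for T = 8, s = 10%. Risks over 8 days are 0.1479 and 0.0769.

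- Before the loss: 0.9 × 0.1479 + 0.1 × 0.0769 = 0.1408, and 0.9 × 0.0769 + 0.1 × 0.0392 = 0.0731.
- After it: 0.9 × 0.1479 + 0.1 × 0.0392 = 0.1370, and 0.9 × 0.0769 + 0.1 × 0.0198 = 0.0712.
- Events lost: 1 − 0.2082/0.2139 = 2.7%.

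| Stay of the other patients (T) | s | Events lost | Power |
|---|---|---|---|
| 4 days | 10% | 4.9% | 77.9% |
| 4 days | 25% | 12.3% | 74.5% |
| 4 days | 50% | 24.6% | 67.9% |
| 6 days | 10% | 3.4% | 78.5% |
| 6 days | 25% | 9.1% | 75.9% |
| 8 days | 10% | 2.7% | 78.8% |
| 8 days | 25% | 7.2% | 76.6% |

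The T = 4 rows are pessimistic, because they treat the minimum projected stay as everyone's stay. The 50% row also needs half the cohort to be at that minimum and recruited at the limit; nothing in the documents points to this.

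**5. Would surface days by group settle it?** Only in part, because surface days stop at injury. Under the hazards above, if every patient had 4 full days available, 7.7% in one group and 3.9% in the other would still show fewer than 4 days, purely because they were injured. A simple count of short exposures by group therefore partly restates the outcome.

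**The case for a change.** The best case for acting is that the ambiguity is real and touches the plan's own rationale. Two natural readings leave 2 days, and only counting from recruitment or randomisation restores the full 4. One sentence and one table row from data already held would cost almost nothing, and an incidence proportion without any person-time is hard to interpret.

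Much of this stands. The start point is missing and the arithmetic is correct. A description of exposure would help a reader.

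It does not amount to a fault in the plan, for three reasons.

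- The randomised comparison is valid under every reading, and no stated power or sample size is made wrong by any of them.
- The Statistical Analysis Plan is written in the past tense, which suggests that enrolment is over. Defining the start point now would probably not change who was enrolled.
- The plan promises no descriptive tables for any variable, so the silence on surface days is not specific to this point. The data are collected, and an analyst reporting such a trial would ordinarily summarise them.

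**Conclusion.** No change is needed. The missing start point is a gap in wording. It can leave about 2 projected days for a minimum-stay patient recruited at the limit, and fewer if the count runs from admission and risk is identified later. It creates no between-group bias and hardly moves the risk ratio (1.96 against 1.98 under the assumed hazards).

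Any loss of power cannot be measured from the documents and is probably small, because 4 days is the minimum projected stay and only late-recruited patients near it are affected. With 10% of patients affected, the loss from an assumed 80% is about 1 to 2 percentage points. With 25% it is about 3.4 to 5.5 points, across assumed stays of 8 down to 4 days for the other patients. These figures rest on constant hazards, equal groups and an 80% benchmark, none of which is in the documents.

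If the authors wish to describe exposure, time from admission or risk identification to randomisation shows the delay directly. Surface days by group are best shown separately for patients with and without injury and labelled as post-randomisation description. That is a reporting choice within the existing plan.

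### Is length of stay cut short in injured participants because it is recorded at the study endpoint?

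*Combined protocol and SAP*

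**What the plan says.** Under Choice of outcomes, injury status is monitored daily "until any of the following endpoints are reached: pressure injury incidence or discharge from hospital". The opening part of the Study protocol closes the Clinical Coordinator's daily recording at the same two events, with data drawn "from assessments, electronic medical records, observations and interviews with clinical staff until pressure injury incidence or hospital discharge".

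Under Choice of covariates, the list is introduced by "Variables that may be associated with the outcome of pressure injuries were recorded and include", and its last item is "Length of stay and number of days on the support surface (recorded at study endpoint"). The document does not define the study endpoint separately from the two events above.

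Severity has its own window: "After an endpoint is reached, the pressure injury severity will be recorded as the highest stage reached prior to discharge". For a deep tissue or unstageable injury that "later becomes stageable as 1, 2, 3, or 4, the latter stage will be recorded".

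The Statistical Analysis Plan contains one analysis: a Pearson chi-square test of incidence in two groups, with and without low air loss. It names no covariate, adjusted model or severity analysis.

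**The concern.** One word, endpoint, appears to serve two windows. If the study endpoint is whichever of injury or discharge comes first, the recorded stay is the full stay for an uninjured participant and the time to injury for an injured one. Length of stay would then be partly determined by the outcome it is listed as a possible correlate of. A table or model using it could suggest that injury goes with short stays when injured patients in fact stayed longer.

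Severity raises a related question. Worst stage before discharge requires someone to look at the injury after it is first found, yet the only stated research schedule stops at that point. If later staging were patchy, severity would be captured unevenly.

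**Working it through.** **The texts side by side.**

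| Item | Window in the protocol |
|---|---|
| Daily injury monitoring and daily data recording | to first injury or discharge |
| Braden scores | daily, to endpoint |
| Length of stay, days on surface | entered at study endpoint (undefined) |
| Severity | highest stage up to discharge, entered after an endpoint |
| Incidence (the chi-square test) | injury yes or no |

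The rows conflict only if the study endpoint means first injury. Three features favour discharge. The bullet gives a time of entry and does not redefine the quantity. The eligibility criterion already uses length of stay in its ordinary hospital sense. Injured participants are still followed to discharge for staging, so their time in the study does not end at injury. None of this is conclusive, because the term is undefined.

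**Size under the literal reading.** The documents give no incidence or stay figures, so every input here is an assumption. Let L be the stay and T the day of injury, with a constant daily risk h independent of L. A participant is injured if T ≤ L, and the recorded stay is min(T, L).

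First set, by exact enumeration: L = 4 + geometric, with h = 0.5%, 1% or 3%. Ranges are over h, in days.

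| Mean stay | Injured, true | Injured, recorded | Uninjured |
|---|---|---|---|
| 6 | 6.9–7.0 | 3.8–4.0 | 5.8–6.0 |
| 8 | 10.0–10.4 | 5.2–5.7 | 7.5–7.9 |
| 12 | 16.4–17.7 | 7.7–9.2 | 10.3–11.7 |

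Incidence runs from 3% to 29%. True stay is 1.0 to 6.1 days longer in the injured; recorded stay is 2.0 to 2.5 days shorter. The sign reverses in all nine scenarios.

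Second set, by simulation: lognormal stay, log-SD 0.5, mean 7, 10 or 14 days, h = 0.5%, 1% or 2%. No uninjured stay is cut, against 86% to 93% of injured stays. With mean 10 and h = 1%, injured versus uninjured is 12.7 versus 9.7 days true and 6.6 versus 9.7 recorded.

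**Is the reversal general?** For small h, the chance of injury is proportional to L, and T given injury is uniform on 1 to L. With mean m and coefficient of variation CV:

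- true mean stay in the injured ≈ m(1 + CV²)
- recorded mean in the injured ≈ [m(1 + CV²) + 1] / 2
- mean in the uninjured ≈ m

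The recorded mean in the injured is below m only if CV² < 1 − 1/m.

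Check with 4 + geometric and mean 8: the geometric part has mean 4 and variance 4 × 5 = 20, so CV² = 20/64 = 0.31, below 1 − 1/8 = 0.875. The formulas give 8 × 1.3125 = 10.5 true and (10.5 + 1)/2 = 5.75 recorded, in line with the table.

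Both sets have low spread (CV about 0.4 to 0.7 and about 0.53). More dispersed stays, simulated with 2,000,000 participants each, behave differently:

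| Assumed stay | CV | h | Injured, recorded | Uninjured |
|---|---|---|---|---|
| Lognormal, mean 8, log-SD 1.0 | 1.3 | 1% | 9.3 | 7.1 |
| 4-day floor, mean 12, log-SD 1.2 | 1.2 | 0.5% | 12.3 | 11.2 |
| Lognormal, mean 8, log-SD 0.8 | 0.94 | 0.5% | 7.7 | 7.7 |

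The reversal is absent in the first two and the difference is about zero in the third. Only the shortening of injured stays is general.

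**Reach into the planned analysis.** The chi-square table needs two facts per participant: surface type and whether an injury occurred. Both are fixed by the first injury or by discharge. Neither length of stay nor stage enters.

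**The case for a change.** The strongest case for a change is that length of stay shares one time stamp with days on the surface, and for days on the surface stopping at injury is a sensible measure of exposure. The text does not separate the two, so a reader cannot be sure which date was used for stay. The covariates were collected because they may relate to injury, so their definitions ought to be usable, and clarification would cost a sentence. That much stands: the term is undefined, and anyone tabulating stay by injury status would need to know the date used.

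The argument weakens when carried further. Harm requires both that staff followed the less natural reading and that someone ran an analysis the Statistical Analysis Plan does not contain. The reversal of direction also needs stays of modest spread, which the documents neither state nor exclude.

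On severity, the protocol expressly provides for recording after an endpoint and gives a rule for injuries that become stageable later. Usual care, with skin inspection twice a day, applies to all groups with no stated stop at injury; certified wound nurses identify injuries; and the electronic medical record is a named source. Only an explicit statement that these supply the later stage is missing. Uneven capture is possible, but nothing in the documents shows it or allows it to be sized.

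**Conclusion.** No change to the plan is needed. This is a gap in wording that analysts would fill sensibly: stay counted to the discharge date, days at risk counted to the first injury, and later stage read from routine skin inspection or the medical record. The effect on the one planned test is nil under either reading.

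The possible distortion is confined to unplanned descriptive or adjusted use of length of stay. In the low-spread scenarios it turns a true excess of 1.0 to 6.1 days in the injured into an apparent deficit of 2.0 to 2.5 days; with strongly skewed stays the direction does not reverse. Those figures rest on an assumed constant daily risk independent of stay and on assumed stay distributions, none of them from the documents. The conclusion would differ if the analysis plan used length of stay or worst stage in a reported comparison, which it does not.

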### **Statistical Analysis Plan**

The effectiveness of reactive support surfaces with and without low air loss were compared. This was done using using a Pearson Chi-Square analysis to test for an association between treatment groups (2 levels - low air loss vs without low air loss) and pressure injury incidence.

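### The low air loss comparison is left unadjusted although Braden total and Moisture are known before randomisation: a modest loss of efficiency, not a validity error

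*Combined protocol and SAP*

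**What the plan says.** **Eligibility (Study protocol).** "New admissions will be screened for the pressure injury risk factors of Total Braden score" of 18 or below, together with "Braden Moisture sub-scale score 1- constantly moist or 2-very moist". A value of each score therefore exists for every participant before allocation. In support of the total-score cut-off the protocol cites a "relative risk of pressure injury of 4.26 (95% CI, 3.27 to 5.55) in a meta-analysis of 31 studies".

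**Randomisation (Study protocol).** Patients are randomised individually to one of seven surfaces at the end of the baseline visit. No stratification by Braden total, Moisture or any other factor is described. How the seven surfaces divide between the two LAL classes is not stated.

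**Covariates (Study protocol, Choice of covariates).** The list opens "Variables that may be associated with the outcome of pressure injuries were recorded and include". One group of items (age, sex, diabetes, nutritional status and others) is marked as recorded at baseline. Braden appears in a separate item: "Pressure injury risk factors (assessed and recorded daily until endpoint): Braden score, Braden subscale scores". No analytic use is given for any item on the list.

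**Analysis (Statistical Analysis Plan).** The whole plan is one "Pearson Chi-Square analysis to test for an association between treatment groups", where the groups are the two LAL classes and the outcome is whether an injury occurred. It contains no regression, stratified test, adjusted estimate or sensitivity analysis. It is written in the past tense.

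**The concern.** The protocol names covariates because they may predict the outcome, and the only analysis uses none of them. Enrolled patients can still differ in risk: totals run downward from 18, and Moisture may be 1 or 2. Without described stratification, the LAL classes can differ by chance in baseline risk. The planned analysis would then give no view of how far the observed difference depends on that.

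Moderate precision and the credibility of the single LAL result are at stake. If the classes turn out visibly unbalanced on Braden total or Moisture, readers will ask for an adjusted result. One chosen after the imbalance is seen carries less weight than one fixed beforehand.

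**Working it through.** **Nothing to reproduce.** The documents give no sample size, event rate, alpha, power or gradient of risk within the enrolled range. The one available check is that the cited relative risk agrees with its interval: √(3.27 × 5.55) = 4.26. Everything below rests on stated assumptions.

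**1. How large could a chance imbalance be?** Assume 400 LAL and 300 non-LAL patients, a Braden SD of 2.3 among those enrolled, and a log-odds slope of 0.1 to 0.3 per point. With that SD, the slopes equal odds ratios per SD of exp(0.23) = 1.26 to exp(0.69) = 1.99.

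- SD of the difference in mean Braden: 2.3 × √(1/400 + 1/300) = 0.176 points.
- A 2-SD imbalance: 0.351 points. Times 0.1 to 0.3 this is 0.035 to 0.105 on the log-odds scale, a shift in the odds ratio of about 4% to 11%. An imbalance that large or larger arises in about 1 trial in 20.

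**2. How does that compare with ordinary sampling error?** At incidence 10% without LAL and 5% with LAL, the same 700 patients give 30 and 20 events.

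- Var(log OR) = 1/20 + 1/380 + 1/30 + 1/270 = 0.0897, so SE = 0.30. The 95% limits lie a factor of exp(1.96 × 0.30) ≈ 1.8 either side.
- Variance due to Braden imbalance: (0.176 × 0.1)² = 0.00031 to (0.176 × 0.3)² = 0.0028.
- Share of the total: about 0.3% to 3%.

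The same sum gives about 0.2% to 1.6% at 5% versus 2.5%, and about 0.6% to 5.7% at 20% versus 10%.

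**3. What does adjustment gain in power?** Trials were simulated with 1:1 allocation, sized for 80% power at two-sided 0.05. Braden total was roughly normal (mean 14, SD 2.2, capped at 18), and 25% of patients had Moisture 1. The same odds ratio applied per SD of Braden total and for Moisture 1 versus 2. The Pearson test was compared with a logistic score test adjusted for both scores, in 1,500 runs per setting.

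| Incidence without / with LAL | n per class | Covariate OR 1.5: unadjusted, adjusted | OR 2.0 | OR 2.5 |
|---|---|---|---|---|
| 5% / 2.5% | 906 | 80.5%, 80.9% | 80.7%, 82.0% | 78.8%, 81.4% |
| 10% / 5% | 435 | 81.7%, 81.5% | 81.1%, 82.9% | 81.1%, 83.8% |
| 20% / 10% | 199 | 81.5%, 81.6% | 79.3%, 82.4% | 79.5%, 84.7% |

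The simulation SE of each power is √(0.8 × 0.2/1500), about 1 point. Both tests were run on the same data sets. Gains run from about 0 at OR 1.5 to between 1.3 and 5.2 points at OR 2.0 to 2.5.

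Type I error lay between 0.042 and 0.061 for both tests in every setting. That is consistent with 5%, given a simulation SE of √(0.05 × 0.95/1500) = 0.006. The adjusted model had the correct form and the two scores were drawn independently; both are simplifications.

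**The case against.** The strongest reply is that nothing is invalid. Under individual randomisation the unadjusted chi-square holds its type I error, and chance imbalance is part of the sampling variation that the test already allows for. In the 400/300 example, Braden imbalance contributes only 0.3% to 3% of the variance of the log odds ratio. Protection from imbalance and variance reduction are largely the same gain, so where one is near nil so is the other. This stands, and it limits the point to efficiency and robustness of interpretation.

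A reader might also infer from the relative risk of 4.26 that Braden total must be a powerful predictor in this trial. The documents do not support that. The figure belongs to the 18-or-below cut-off, and every participant is at or below 18. No gradient within that range is given, and Moisture is reduced to two levels.

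The covariate list also shows Braden as a daily measure, apart from the items marked as baseline. This stands too. Eligibility shows that a pre-randomisation value exists, but the analysis would have to name it. Nor are the scores discarded: they continue to be recorded, and only the analysis leaves them out.

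Finally, the plan's past tense suggests that the analysis may be finished, in which case an added model cannot be called pre-specified. This affects the label, not the usefulness of the result.

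**Conclusion.** The point holds in a limited form. The only planned analysis ignores two scores that are known before randomisation, listed among the covariates and not described as stratification factors. The consequence is a modest loss of efficiency and of protection against chance imbalance: from about nil if the scores predict weakly within the enrolled range to a few power points if they predict strongly. That size depends wholly on assumed incidence, trial size, class split, Braden spread and covariate strength.

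It would be wrong to conclude that the LAL comparison is biased or that its p-value is unreliable. It would be equally wrong to treat adjustment as a complete cure: it deals only with the covariates in the model, and few events limit how many it can carry.

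**What to change.** Keep the Pearson chi-square and add one adjusted comparison of LAL class:

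- **Covariates.** Use the last Braden total (linear) and the last Moisture score (1 versus 2) recorded before randomisation. Say so explicitly, since recruitment can follow the finding of moisture risk by up to 48 hours and Braden is scored daily. Age is optional.
- **Model and estimate.** Fit a logistic regression of pressure injury on LAL class and these covariates. Average the predicted risks over all participants under each class, and report the resulting risk difference or risk ratio with its 95% CI beside the unadjusted result.
- **If events are few.** Use a Mantel-Haenszel analysis stratified on the pre-randomisation scores instead. In the 700-patient example, 5% versus 2.5% gives only 15 + 10 = 25 events.
- **Exclusions.** Do not adjust for daily scores after randomisation, length of stay or days on the surface, because the assigned surface may affect them.
- **Label.** Call the analysis post hoc if outcome data by group had been seen before it was specified.

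The cost is a short addition to the plan and one extra model on scores already obtained. It needs no further patients or procedures. The drawbacks are a second result to report and a restricted covariate set if events are few.
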